### **c. End of participation**

Participation will be completed upon completion of the procedures described above. Because participants are healthy volunteers, the only information to be shared with participants would be incidental findings from their medical exam.

## **5. Management of Data and Samples**

### **a. Storage**

After every scanning and behavioral session, all data collected will be de-identified and coded. Data recorded manually on paper will be entered into computer files. All de-identified data will be stored on password protected NCCIH computers and on secure lab servers hosted by NINDS. All paper forms completed by the subjects will be securely kept in locked drawers in the laboratory/office space of the Principal Investigator. The lab is locked when not occupied. Only study investigators will have access to the data.

### **b. Data and sample sharing plan**

As no large scale genomic data will be acquired during the course of this protocol, this protocol is not subject to the NIH Genomic Data Sharing (GDS) policy.

Data will be shared with qualified investigators at NIH or other institutions, including our collaborators on this study, [name] (Linkoping University, Sweden) and [name] (Sahlgrenska Academy at University of Gothenburg).

Data may also be shared with collaborating laboratories at NIH or outside of NIH and/or submitted to NIH-designated repositories and databases if consent for sharing was obtained. Repositories receiving data from this protocol will be restricted access.

Data will be stripped of identifiers and may be coded (“de-identified”) or unlinked from an identifying code (“anonymized”). When coded data is shared, the key to the code will not be provided to collaborators, but will remain at NIH. Data and samples may be shared with investigators and institutions with an FWA or operating under the Declaration of Helsinki (DoH) and reported at the time of continuing review. Sharing with investigators without an FWA or not operating under the DoH will be submitted for prospective IRB approval. Submissions to NIH-sponsored or supported databases and repositories will be reported at the time of Continuing Review. Submission to non-NIH sponsored or supported databases and repositories will be submitted for prospective IRB approval.

Required approvals from the collaborating institution will be obtained and materials will be shipped in accordance with NIH and federal regulations.

NCCIH specific information on data sharing:

Samples and data may be shared with:

1. Qualified investigators at NIH: For this purpose, investigators will first agree to a data use policy and data will be transferred via methods that limit the chance of others gaining access, such as using a secure file transfer protocol (*sftp*) or restricted access file hosting sites such as [nihcesaev.cit.nih.gov](http://nihcesaev.cit.nih.gov).
2. Data will be transferred using secure file transfer protocols. Investigators will be allowed to download data after they agree to a data use policy. Some data repositories have their own data use agreement, while others allow the submitter to provide his/her own data use policy. Examples of such repositories include the NITRC (Neuroimaging Informatics Tools and Resources Clearinghouse, [www.nitrc.org](http://www.nitrc.org)), the XNAT Central (eXtensible Neuroimaging Archive Toolkit, [central.xnat.org](http://central.xnat.org)), OpenfMRI (OpenfMRI.org), PAIN (Pain and Interceptive Imaging Network, [www.painrepository.org](http://www.painrepository.org)), INCF Dataspace (International Neuroinformatics Coordinating Facility, [www.incf.org](http://www.incf.org)), 1000 Functional Connectomes and NIDAG (Neuroimaging Data Access Group, [www.nidag.org](http://www.nidag.org)). New data repositories are being created periodically with the intent to facilitate collaboration between research groups with distinct areas of expertise and thus, data collected under this protocol may be contributed to other data repositories not explicitly listed here. Data will only be placed in repositories where access to the data can be restricted to people who accept the data use guidelines and have an account and password that are linked to a valid email address.
  - o Demographic data (age and sex) and behavioral data such as performance on a task, may also be shared. As this protocol concerns studies healthy volunteers, the risk to a participant from sharing their

de-identified data is minimal. Depending on the situation, a Global Unique Identifier (GUID) code may be attached to an individual's data prior to sharing or uploading to a repository. When GUID codes are used, only researchers who already have access to someone's personal information can access the code.

## 6. Additional Considerations

None

## 7. Risks and Discomforts

A risk of the screening procedures is the results of the drug tests, which will remain documented in the participant's medical record. However, the participants will be informed of this during the telephone pre-screening procedure and asked if they want to continue. If they choose to continue, they will be reminded again during the consenting process.

### **Risks associated with ischemic-compression nerve block:**

Ischemic-compression blocks are considered safe when administered for under 2 hours at 250 mmHg in adults, including in elderly adults and in patients with medical comorbidities [19]. Complications are rare and arise most often observed the use of tourniquets during surgical procedures, in patients with medical conditions [20]. Ischemic-compression blocks have been used in several experimental studies of sensory perception without any reported adverse effects [3, 13, 21]. Participants are not always able to tolerate the block for a full session due to pain or discomfort at the site of the blood pressure cuff (e.g. in one study a number of participants ended their 1-hour session early due to pain or discomfort, but all subjects tolerated a minimum of 27 minutes [13]). Vasovagal responses are another possible side effect due to anxiety or changes in blood pressure. Punctate hemorrhage of the skin or shearing of the skin are other minor risks. When the cuff is released, painful paresthesia may occur [22]. By releasing the pressure very slowly (e.g. over the course of more than a minute), as we will in the current study,

we have found that paresthesia is minimized and does not cause more than very mild discomfort.

There is a risk of inducing a seizure due to blood pressure changes in an individual with a history of seizure disorder, so these individuals will be excluded. In addition, due to the theoretic risk of deep vein thrombosis (evidence for this risk is mixed; [20, 23]), individuals with a first-degree family history of blood clots, clotting or circulatory disorders will be excluded.

Nerve injury and swelling, metabolic dysfunction, and muscle injury are possible but rare effects of prolonged compression during prolonged surgical procedures [23]. Therefore, we will minimize compression time, releasing the cuff within 1 hour, and monitor the subject for any adverse physical or psychological responses. These side effects have not been reported to our knowledge during short-duration experimental procedures.

Participants will be screened and excluded for cardiovascular disease, or drugs that can produce adverse cardiovascular effects. The investigators will closely monitor subjects during each study session for any signs of nausea or discomfort. In the case of an acute adverse event, medical evaluation and treatment recommendations will be provided by the LHPs on this protocol. 911 will be called if immediate treatment is required.

Participants are to be referred to their local physician if further evaluation or treatment is necessary. Participants will be followed weekly by a phone call until resolution of AE's.

### **Risks and discomforts associated with heat and cool stimuli**

The nature of the study requires the application of warm and cool stimuli that can become painfully hot or cold if not perceived at typical thresholds. However, these stimuli have been used in previous studies, have proven to be easily tolerated, and do not cause permanent tissue damage. Slight reddening or darkening of the skin may occur. This is transient and disappears after termination of the testing. Heat pain stimulation has been used extensively without any long-term adverse effects [17, 18, 24].

### **Risks and discomforts associated with vibration, pinprick, and compression stimuli**

There are no known risks of the vibration or pinprick stimuli other than possible minor discomfort. Pressure stimuli may be uncomfortable to some participants, but the pressure will be lower than a standard blood pressure cuff and familiar to all participants. Repeated inflation could dislodge any active blood clots in the participant's arm, so all participants will be checked during medical screening to ensure they do not have any clinical signs of clots present.

## **8. Subject Safety Monitoring**

Participants will be monitored by the study investigators during the study visit for study outcomes and adverse events. All subjects will be instructed about, and receive practice with, all sensory testing before it is administered, and adequate comprehension of the instructions for each test will be insured by the test examiner.

During the nerve block, at least one experimenter will remain in the room with the subject at all times. A LHP will be in the clinic at all times available for consultation. The participant's vital signs will be checked before and after the nerve block. Study staff will monitor subjects during participation and subjects will be encouraged to tell experimenters of any discomfort or concerns. If apparatus, etc., cannot be adjusted to relieve discomfort that the subject cannot tolerate, the experiment will be stopped. Subjects may withdraw at any time.

Participants can withdraw from this study at any time and for any reason without loss of benefits or privileges to which they are otherwise entitled or prohibition from enrolling in other clinical protocols. Investigators can remove a participant from the study if an exclusionary condition develops, if the investigator believes that continuation is not in the best medical interest of the subject, or if the subject is unable to comply with study requirements. Sessions may also be terminated early due to factors that do not directly influence subject safety, such as technical difficulties (e.g. equipment malfunction, computer issues), if schedule conflicts arise (e.g. participant arrives late or needs to

leave early; delays in Clinical Center waiting time, time to process lab orders and lab results). When sessions are terminated early, participants may be asked whether they wish to reschedule. Participants who terminate early because of not tolerating the block well will not be rescheduled.

#### **A. Withdrawal Criteria**

Participants can withdraw from this study at any time and for any reason without loss of benefits or privileges to which they are otherwise entitled, or prohibition from enrolling in other clinical protocols. Investigators can remove a participant from the study if an exclusionary condition develops, if the investigator believes that continuation is not in the best medical interest of the subject, or if the subject unable to comply with study requirements.

#### **B. Criteria for Stopping study**

In all subjects, individual subject sessions will be stopped if requested by participants or if the investigators feel it is in the best interest of the participant.

## **9. Outcome Measures**

### **Primary outcome measures**

The primary outcome is the change or difference score (pre to post) in intensity ratings of deep pressure measured before and after loss of A-beta-associated sensations on the affected arm versus the unaffected arm (e.g. compared between arms by a paired t-test at the group level).

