#### d. Study procedures

Participants eligible to proceed will be asked to complete a single session, in the NIH Clinical Research Center.

An LHP will review eligibility criteria at the beginning of each session, to confirm that participants remain eligible and meet day-of-study criteria (5-10 minutes). Then, the nerve block procedure and sensory testing will be performed as depicted in **Figure 1. Study Flow** and described in detail below (approximately 1 hour, all procedures for research purposes):

[figure not shown]

Figure 1. Study Flow

Each nerve block session will follow approximately the timeline shown. Timing is approximate as nerve blocks progress at different speeds for different individuals.

Baseline affective touch testing will be performed on both arms (ratings of the intensity and pleasantness of slow brushing and deep pressure). The tourniquet will be placed by a LHP. Sensory testing will be conducted regularly to monitor block progression and loss of A-beta-associated sensation. When A-beta associated perception has been substantively eliminated, ratings of slow brushing and deep pressure (affective touch) will be repeated on each arm/hand. Sensory monitoring will continue and affective ratings may be repeated if further A-beta or A-delta percepts are lost before C-fiber function (loss of warm perception; this separation is not always observed; [14]). Testing is likely to be completed within 30-40 minutes from block placement. The nerve block will be removed by 60 minutes from placement.

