### **Details of Ischemic-compression nerve block**

An ischemic-compression block (see [Figure 2](#) below) will be placed to eliminate A-beta associated sensation. Ischemic-compression blocks affect large myelinated fibers before unmyelinated fibers are affected [14]. The subject will hold one arm over their head for approximately one minute and the LHP will exsanguinate the arm. Half the subjects will be tested on the dominant arm and half on the non-dominant arm to avoid confounds in arm dominance and affective responses. The LHP will then inflate tourniquet to approximately 100mmHg above the subject's systolic blood pressure (BP) (e.g. [13, 14]). The subject will then rest their arm comfortably on a pillow on a table placed in front of them. Sensory testing will be conducted with sight occluded and white noise or similar sounds via headphones to eliminate visual and auditory cues in the sensory tasks.

[figure not shown]

Figure 2. An ischemic-compression block

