### **Details of Sensory testing paradigm**

Ratings of intensity and pleasantness of pressure and brushing: At baseline and after loss of sensation associated with A fibers, perception of deep pressure and gentle brushing will be tested on both arms. Deep pressure will be administered to the hand and wrist for approximately 20 seconds using a hand massager that applies oscillating pressure. Gentle brushing will be administered to the hand/forearm by a trained experimenter at a rate of approximately 3cm/second for approximately 15 seconds. Participants will rate intensity and pleasantness of each sensation on VAS scales with anchors of “no sensation” to “highest possible intensity” and from “extremely unpleasant” to “neutral” (midpoint) to “extremely pleasant.” Nearly identical VAS scales have been successfully used in our lab in numerous previous studies to distinguish the intensity versus pleasantness of sensory stimuli (e.g. [16, 17]). If cool perception is lost after light touch (not concurrently), A-delta fibers may be isolated and ratings can be collected again. Loss of cool and light touch often coincide, however [14]. Ratings of bad mood and anxiety will also be collected. They will be rated verbally on 0-10 scales (0 = none; 10 = worst you have experienced).

After placement of the tourniquet but before elimination of A-beta associated sensation, sensory testing will be conducted to monitor the block progression. Sensory testing will be conducted nearly continuously, which each test conducted approximately every ~1-2 minutes. All testing will be conducted distal to the block. The tests conducted during sensory monitoring may include the following:

Vibration perception (A-beta): A custom vibration device administering ~200 Hz vibration to the skin of the palm will be set for a random duration between 1-6 seconds. Participants will press a button (or similar response) when they perceive the onset and offset of the vibration.

Warm (C-fiber) and cool (A-delta) perception: Heat stimuli will be administered by the trained experimenter to the ventral surface of the forearm or palm using a contact

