#### Behavioral Data

All behavioral data will be analyzed using SPSS or similar statistical package. A significance level of  $p < 0.05$  will be adopted for all analyses.

For the primary and secondary outcomes, we will use paired t-test or equivalent nonparametric test to evaluate the effect of the nerve block

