### b. Power analysis

In order to yield meaningful statistical analyses of the psychophysical data, and specifically for our primary outcome measure, we estimate that the sample size required to complete the study would be 12 healthy participants. G\*Power (<http://www.gpower.hhu.de>) was used to compute the necessary sample size. In our recent study of deep pressure perception (manuscript in preparation; data available upon request), the same oscillating deep pressure sequence was rated as an intensity  $M = 4.2$  (scaled to our 0-10 scale); we expect intensity to drop at least 2 points on our 0-10 rating scale (likely more since patients lacking A-beta fibers had no perception of deep pressure in our previous study, Case & [name] et. al., under review). In our previous study healthy participants rated the same deep pressure sequence on two different days and the standard deviation of the change in their rating from Day 1 to Day 2 was 1.7. Based on a

2-point change (due to blocking A-beta fibers which should fully eliminate sensation) and a standard deviation for within-subject rating change scores of 1.7, we expect a Cohen's effect size  $d = 1.17$ . Setting statistical power to 95% and Type I error probability to  $\alpha=0.05$ , 12 subjects would be required to complete the study. We expect up to a 50% dropout rate of participants based on prior NIH studies and the discomfort of prolonged nerve blocks found in other studies [13]. Thus, we will enroll up to 24 participants and dropouts will be replaced.

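### Should the primary comparison adjust for the baseline ratings by regression instead of using a paired test on change scores?

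*Combined protocol and SAP*

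**What the plan says.** Section 9 (Primary outcome measures) sets the endpoint: "The primary outcome is the change or difference score (pre to post) in intensity ratings of deep pressure", on the affected versus the unaffected arm, for example "compared between arms by a paired t-test at the group level". Section 10.a (Behavioral Data) repeats the choice for primary and secondary outcomes: "we will use paired t-test or equivalent nonparametric test to evaluate the effect of the nerve block". No baseline covariate appears in either section.

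The baseline data exist. Section 4.d states that "Baseline affective touch testing will be performed on both arms", and the sensory testing details in the same section add: "At baseline and after loss of sensation associated with A fibers, perception of deep pressure and gentle brushing will be tested on both arms".

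On the choice of arm, the nerve block details in Section 4.d say: "Half the subjects will be tested on the dominant arm and half on the non-dominant arm". They do not say that the arm is assigned at random.

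The power analysis in Section 10.b uses a drop of 2 points on a 0-10 scale, which it presents as a minimum. It takes its SD from an earlier study in which healthy participants rated the same pressure sequence on two days: "the standard deviation of the change in their rating from Day 1 to Day 2 was 1.7".

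**The concern.** A change score fixes the baseline coefficient at 1. If a participant's between-arm difference at baseline is mostly noise, subtracting it adds that noise to the endpoint. Regressing the later between-arm difference on the baseline one, and testing the intercept at a zero baseline difference, lets the data choose the coefficient. Where the before/after correlation is low, this removes up to half of the error variance.

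The study aims for only 12 completers, undergoing a painful block with up to half expected to drop out, so wasted precision would be costly. The adjusted analysis needs no new measurements. In the most favourable setting examined below, it would lift power from about 75% to about 93%.

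**Working it through.** **The plan's own figure.** Inputs from Section 10.b: effect 2, SD 1.7, alpha 0.05, power 95%. d = 2/1.7 = 1.18 (stated as 1.17). An exact two-sided paired t-test (noncentral t, n - 1 degrees of freedom) gives 95.7% to 95.9% power at n = 12 and 93.7% to 93.9% at n = 11. The stated 12 reproduces.

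**Quantities the documents do not give.** Two are needed, and both are assumptions here.

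- The SD of the between-arm difference of changes. The 1.7 describes one change; the primary contrast is a difference of two. If c is the correlation of the two arms' changes, SD = 1.7 x sqrt(2(1 - c)): 1.70 at c = 0.5, 2.08 at c = 0.25, 2.40 at c = 0.
- The correlation r between the before and after between-arm differences, taken from 0 to 0.9.

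**Error variance.** Let s be the common SD of the before and after between-arm differences.

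- Change score: 2s²(1 - r).
- Regression residual: s²(1 - r²).
- Ratio: (1 + r)/2.

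Estimating the slope inflates the variance by about 1 + 1/(n - 3) = 10/9 and costs one degree of freedom (11 to 10). Setting (1 + r)/2 x 10/9 = 1 gives r = 0.8. With the lost degree of freedom, break-even is near r = 0.75.

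**Power (%), n = 12, 2-point drop, two-sided 5%.** Change-score figures are exact; regression figures are simulated under bivariate normality with equal variances.

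| SD | Change score | Regression, r = 0 | 0.3 | 0.5 | 0.7 | 0.8 | 0.9 |
|---|---|---|---|---|---|---|---|
| 1.70 | 95.9 | 99.7 | 98.8 | 97.7 | 96.3 | 95.4 | 94.4 |
| 2.08 | 85.8 | 97.7 | 93.8 | 90.6 | 87.0 | 85.1 | 83.2 |
| 2.40 | 74.7 | 93.4 | 86.3 | 81.3 | 76.7 | 74.3 | 72.0 |

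At SD 1.70 the change runs from 99.7 - 95.9 = +3.8 to 94.4 - 95.9 = -1.5 points. It cannot exceed 100 - 95.9 = 4.1. At SD 2.40 it runs from +18.7 to -2.7.

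**A larger drop.** Section 10.b thinks more than 2 points likely, and expects the block to abolish a sensation rated 4.2 on average. For a 3-point drop at SD 2.40, the change-score test already has about 97.5% power, and adjustment changes it by +2.3 to -1.2 points. For 4.2 points the change is about zero.

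**What the regression assumes.** Suppose the to-be-blocked arm is systematically rated b points higher, before and after. The change score cancels b. In the regression the slope is r, so the expected intercept is b(1 - r) minus the drop. With b = 0.5 and r = 0, a true drop of 0 appears as +0.5, and a true drop of 2 appears as 1.5.

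- Type I error at r = 0 / 0.3 / 0.5: about 14%, 8%, 6% (SD 2.40); about 21%, 11%, 8% (SD 1.70). The paired test stays at 5%.
- Power for a 2-point drop, over r from 0 to 0.9: 69-71% against 75% (SD 2.40); 80-81% against 86% (SD 2.08); 91-93% against 96% (SD 1.70). The regression is below the paired test at every r tried.

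If the blocked arm is instead the lower one at baseline, the regression's power rises, but only because the same bias then adds to the drop.

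**Could the trial check the assumption?** At SD 2.40 and r = 0, s = 2.40/sqrt(2) = 1.70. The 95% confidence interval for the mean baseline difference is then ±2.20 x 1.70/sqrt(12) = ±1.08. At SD 1.70, s = 1.20 and the interval is ±0.76. Neither could exclude 0.5 points when the observed mean is zero.

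**The case for a change.** The best case for adjustment is that the favourable corner is a natural one. If each rating is a stable person effect plus independent noise, a single-change SD of 1.7 implies SD 2.40 and r = 0 together, where the gain is largest. A high r would need stable, person-specific differences between a healthy person's two arms, and the documents describe none. The pay-off is lopsided, about 19 points up against 3 down. The dominance split supports equal baselines on average: with a dominance offset of 0.5 points, an even 6/6 split keeps the regression's type I error at 4.3% to 4.9% (SD 2.40, r from 0.5 down to 0). The paired test could stay as a supporting analysis.

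Part of this stands. Adjustment is a legitimate option, and under that noise model with equal expected baselines the gain is real. But the 1.7 is a between-day SD. Day-to-day shifts shared by both arms would lower the between-arm SD and shrink the gain. The 75% base power at SD 2.40 arises because the sample size uses the SD of one change for a difference of two; that is a sample-size question, and leaving out a covariate did not cause it. The split covers dominance only, the arm is not said to be randomised, and with replacement of dropouts an even split among the 12 completers is not assured. Making the regression primary would put the test that depends on equal baselines ahead of the one that does not.

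**Conclusion.** The concern does not hold. The paired change-score comparison is valid, uses the baseline rating of each arm, and needs no assumption about how the arms compare before the block. Replacing it by a baseline regression would gain or lose power depending on two quantities the documents do not give: about +4 to -2 points at SD 1.70 and about +19 to -3 at SD 2.40, with break-even near r = 0.75, and 2.3 points at most for a 3-point drop at SD 2.40. Against that stands the loss of type I error control, and possibly of power, if the arms differ systematically at baseline by as little as half a point. These figures assume 12 completers, two-sided 5% testing, normality and equal before and after variances. Equal variances are doubtful if the block pushes ratings to the floor of the scale. Choosing robustness over a conditional gain in efficiency is a reasonable design decision, and nothing in Sections 9 or 10 needs changing on this account.
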